## 10.2 Analysis of Daily Efficacy Measurements

For daily efficacy

CCI

The text "CCI" is followed by four lines of redacted content, represented by black bars of varying lengths.

For Period 1 or the entry value for Period 2, the rolling weekly average score is calculated starting from the first day when a measurement was available to the last day with a measurement, Let  $P_{m-6}, P_{m-5}, \dots, P_{m-1}, P_m$  be the daily total scores from day  $m - 6$  to day  $m$ , and  $N_m$  be the number of days with non-missing pain scores from day  $m - 6$  to day  $m$ , then the rolling weekly average for Day  $m$  is:

$$\frac{\sum_{i=m-6}^m P_i}{N_m}$$

If the values from four or more days of the seven-day period are missing, then the rolling weekly average of Day  $m$  will be set to missing. If more than one assessment is included on the same day, the assessment associated with the worst condition on that day will be chosen as the daily score.

---

Analysis value for a given visit will be selected from rolling averages based on analysis window conventions, after dropping the rolling averages from Day 1 – 6 for Actigraphy, and Day 1 – 7 for other assessments, in each period.

For the visits where the questionnaire is completed at the site, scores from single clinic visits will be used as the analysis value.

### **10.3 Primary Efficacy Analysis**

The primary efficacy variable is the percent (%) change from Baseline in EASI score at Week 16. The analysis of the primary efficacy variable will be carried out in ITT\_1 with the LOCF missing data imputation. The dose-response relationship will be evaluated by MCP-Mod method.

### **10.4 Secondary Efficacy Analyses**

The secondary efficacy variables include:

- Proportion of subjects achieving an EASI 75 response, defined as at least a 75% reduction in EASI score, at Week 16 relative to Baseline
  - Proportion of subjects achieving an IGA 0 or 1 response at Week 16
  - Percent change from Baseline in pruritus numerical rating scale (NRS) by week
  - Percent change in EASI score from Baseline at Week 8
  - Percent change in SCORAD score from Baseline at Weeks 8 and 16
  - Proportion of subjects achieving EASI 50/75/90 response at Weeks 8 and 16
  - Proportion of subjects achieving SCORAD 50/75/90 response at Weeks 8 and 16
  - Change from Baseline in BSA at Week 16
  - Percent change from re-randomization in EASI score in Period 2
  - Time to loss of EASI 50 response among those who were re-randomized as EASI 75 responders at Week 16
-

- Summary of EASI 75 at all visits in Period 2 among those who were re-randomized as EASI 75 non-responders at Week 16
- Proportion of subjects with reduction of  $\geq 4$  from Baseline in pruritus NRS among subjects with a baseline of  $\geq 4$

## 10.5 Exploratory Variables

The following endpoints will be analyzed at all visits or weeks that the assessments are collected, except for daily assessments where results based on a rolling average by week will be presented.

- Time to EASI 50/75/90 and IGA "0" or "1" response in Period 1.
  - Proportion of subjects achieving EASI 50/75/90/100 response.
  - Proportion of subjects achieving SCORAD 50/75/90 response.
  - Change from Baseline in POEM at Weeks 4, 16, 24 and 40.
  - Change from Baseline at Weeks 4, 16, 24 and 40 in MOS Sleep Scale (Sleep Disturbance Score, Snoring Score, Short of Breath Score, Sleep Adequacy Score, Sleep Somnolence Score, Sleep Problems Index 1 Score, Sleep Problems Index 2 Score, Optimal Sleep Score, and Sleep Quantity Score).
  - Change from Baseline at Weeks 16 and 40 in Asthma Symptoms Questionnaire.
  - Change from Baseline at Weeks 16 and 40 in Daytime Nasal Symptoms Questionnaire.
  - Change from Baseline in total sleep time per night (TST min), Sleep Efficiency (%), Wake After Sleep Onset (WASO), number of scratching events per hour, mean activity during rest (sleep) periods as measured by actigraphy, by week until Week 40 and by visit thereafter.
  - Change from Baseline in ADERM-SS and ADERM-IS by week until Week 40 and by visit thereafter.
  - Change from Baseline in PGIS.
  - Proportion of subjects with a DLQI 0 or 1 response.
-

- Change from Baseline in DLQI.
- Change from re-randomization in EASI score in Period 2.

Primary and secondary variables will also be evaluated at all scheduled visits.

The efficacy of rescue will be summarized for subjects who received the rescue medication.

Due to collection issues in DLQI Question 7, the corresponding secondary endpoints have been changed to exploratory variables and the answers to Question 7 will be removed from the analyses. Of note, correction to the DLQI ePRO device has been corrected while the study is ongoing. Additional analyses based on correct DLQI data may be performed.

The EASI overall score, IGA and pruritus NRS score will be summarized at Baseline and Week 16 for subjects from Japan, with the percentage changes in EASI and pruritus NRS from baseline to Week 16.

In addition to the overall EASI score, body region EASI scores will be analyzed. The analysis will include all the four body component scores for head/neck, trunk, upper and lower extremities. Body component EASI scores are determined by multiplying the total of erythema, edema/papulation, excoriation, and lichenification scores within each body region by the area score.

EASI body region score = (erythema score + edema/papulation score + excoriation score + lichenification score)\*area score

In addition, the SCORAD affected areas of head/neck and genitals will be analyzed along with the overall score.

Information on the scoring and missing value handling the SCORAD and Patient Reported Outcomes (PROs) is presented in [Appendix A](#) and [Appendix B](#). The types of PROs include POEM, MOS, pruritus NRS, PGIS, ADerm-SS, ADerm-IS, Asthma

---

Symptoms Questionnaire, Daytime Nasal Symptom Questionnaire and ActiGraphy measurements.

MCP-Mod will also be performed for proportion of subjects achieving EASI 75 and achieving IGA 0 or 1 at Week 16.

## **10.6 Handling of Multiplicity**

Multiplicity adjustments are not performed in this Phase 2b study.

## **10.7 Efficacy Subgroup Analysis**

To evaluate the impact of baseline characteristics, subgroup analyses will be performed at Week 16 for the primary efficacy variable, percent change in EASI from baseline, and two of the secondary efficacy variables, proportion of subjects achieving EASI 75 and proportion of subjects achieving IGA of 0 or 1. The subgroups are defined by each of the demographic factors on age, gender, body mass index (BMI), race, weight and geographical region as shown in [Table 14](#) below. Additional subgroup analysis based on baseline characteristics may be conducted.

If any of the resulting subgroups has fewer than 5 subjects, the subgroup analyses for that variable will not be presented.

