5.2.1 Inclusion Criteria

1. Adult male or female, ≥ 18 and ≤ 75 years old at Screening.

2. Atopic dermatitis with a diagnosis confirmed by a dermatologist (according to the Hanifin and Rajka criteria); and also onset of symptoms at least 1 year prior to baseline.
3. Moderate to severe AD defined by an EASI ≥ 16 , BSA $\geq 10\%$ and an IGA score ≥ 3 at the Baseline visit.
4. Documented history (within 1 year prior to the screening visit) of inadequate response to treatment with topical corticosteroids (TCS), or topical calcineurin inhibitors (TCI), or for whom topical treatments are otherwise medically inadvisable (e.g., because of important side effects or safety risks).
5. Twice daily use of an additive-free, bland emollient for at least 7 days prior to Baseline.
6. A negative serum pregnancy test for all female subjects at the Screening Visit and a negative urine pregnancy test for all female subjects of childbearing potential at the Baseline Visit prior to administration of first dose of study drug. Note: subjects with borderline pregnancy test at Screening must have a serum pregnancy test ≥ 3 days later to document continued lack of a positive result.
7. If female, subject must be postmenopausal OR permanently surgically sterile OR for Women of Childbearing Potential practicing at least one protocol specified method of birth control (Section 5.2.4), that is effective from the Baseline visit through at least 30 days after the last dose of study drug.

If male and subject is sexually active with a female partner(s) of childbearing potential, he must practice the protocol specified contraception from the Baseline visit through at least 30 days after last dose of study drug (Section 5.2.4).

Additional local requirements may apply. Refer to [Appendix P](#) for local requirements in Canada.

8. Subjects must voluntarily sign and date an informed consent, approved by an Independent Ethics Committee (IEC)/Institutional Review Board (IRB), prior to the initiation of any screening or study-specific procedures. For subjects in Japan

only: if a subject is under 20 years of age, then the subject and their parent or legal guardian must voluntarily sign and date an informed consent.

Rationale for Inclusion Criteria

- | | |
|-------|--|
| 1 – 5 | To select the appropriate subject population |
| 6 – 7 | The impact of ABT-494 on pregnancy and reproduction is unknown |
| 8 | In accordance with harmonized Good Clinical Practice (GCP) |

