#### **4.2 Design Diagram**

This is an 88-week Phase 2b, randomized, double-blind, parallel-group, placebo-controlled multicenter study of safety and efficacy of upadacitinib in adult subjects with moderate to severe AD.

The duration of the study will be up to 88 weeks and will include a 35-day maximum screening period, a 16-week double-blind treatment period (Period 1) and a 72-week double-blind treatment period (Period 2). In addition, a 30-day follow-up visit (or phone

---

call if a visit is not possible) should occur to determine the status of any ongoing AEs or serious adverse events (SAEs), or the occurrence of any new AEs/SAEs.

**Period 1:** A 16-week double-blind, placebo-controlled treatment period during which subjects will be randomized in a 1:1:1:1 ratio to one of four treatment groups:

- Group 1: upadacitinib 7.5 mg once daily (QD) for 16 weeks
- Group 2: upadacitinib 15 mg QD for 16 weeks
- Group 3: upadacitinib 30 mg QD for 16 weeks
- Group 4: Matching Placebo for 16 weeks

Randomization will be stratified by geographic region (US/PR/Canada, EU/AUS, and Japan). Enrollment in Japan will be capped at 10% of subjects (4 subjects per group).

In Period 1, discontinuation from study drug will be mandatory for any subject with an Eczema Area and Severity Index (EASI) score worsening of 25% or more compared with their baseline EASI score at any 2 consecutive scheduled study visits from Week 4 to Week 12.

**Period 2:** a 72-week double-blind, placebo controlled treatment period during which subjects who complete Period 1 will be re-randomized at Week 16 within their original treatment group assignments to either upadacitinib or placebo into a 72-week double-blind, placebo controlled treatment period in a 1:1 ratio as shown in [Figure 1](#) (study design). Randomization will be stratified by geographic region and the improvement of EASI score by at least 75% (EASI 75 response) at Week 16. At the Week 16 visit, all subjects will be re-randomized as follows into Period 2:

- Group 1 in Period 1: upadacitinib 7.5 mg QD or matching placebo for 72 weeks
  - Group 2 in Period 1: upadacitinib 15 mg QD or matching placebo for 72 weeks
  - Group 3 in Period 1: upadacitinib 30 mg QD or matching placebo for 72 weeks
-

- Group 4 in Period 1: upadacitinib 30 mg QD or matching placebo for 72 weeks

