**Figure 1. Study Design Schematic**

### 4.3 Sample Size

Approximately 160 subjects will be randomized to the four treatment groups in a ratio of 1:1:1:1. The sample size for this study is based on the percent change in EASI from baseline at Week 16. Assuming a percent change in EASI from baseline at Week 16 of 35, 45, 60, and 70 in the placebo, 7.5 mg, 15 mg, and 30 mg arms with a standard deviation 40 and a maximum efficacy of 80, a sample size of 40 subjects per treatment group is sufficient to test for the presence of a dose response signal, to select the best dose response model for the observed data out of a pre-specified set of candidate models, and to estimate target doses of interest (e.g., the minimum effective dose, MED) via modeling

using the MCP-Mod (Multiple comparison procedure and modeling) approach. This approach provides 99% average power to detect a dose effect at the 5% level of significance (one-sided) with the linear,  $E_{\max}$ , exponential, logistic and  $\text{sig}E_{\max}$  models pre-specified as likely candidates to characterize the dose-response for upadacitinib for the percent change in EASI.

A sample of size 40 per group provides 97% power to detect a significant difference between 30 mg QD and placebo, and 78% power to detect a significant difference between 15 mg QD and placebo at the two-sided level of significance of 5.0%.

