**Table 14. Subgroup Analysis**

Subgroup Factor	Categories
Age	< 40 years old ≥ 40 – < 65 years ≥ 65 years old
Sex	Male Female
BMI	< 25 ≥ 25 – < 30 ≥ 30 – < 40 ≥ 40
Race	White Asian Other
Weight	< median ≥ median
Geographic region	US/PR/Canada EU/AUS Japan

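### SAP 10.7 drops every subgroup result for a factor when one Table 14 category has fewer than 5 subjects, so a rare BMI, race or possibly age class can remove the whole factor

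*SAP*

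**What the plan says.** SAP 10.7 evaluates the influence of baseline characteristics on three Week 16 outcomes: percent change in EASI, EASI 75 and IGA 0/1. The factors are age, sex, BMI, race, weight and region, with the classes listed in SAP Table 14. BMI has four ("< 25 ≥ 25 – < 30 ≥ 30 – < 40 ≥ 40"), age has three ("< 40 years old ≥ 40 – < 65 years ≥ 65 years old"), race has White, Asian and Other, and region has three including Japan. Weight is split at the median.

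The section closes with a size rule: "If any of the resulting subgroups has fewer than 5 subjects, the subgroup analyses for that variable will not be presented". The trigger is a single class; the consequence falls on the variable.

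Three other places bear on it:

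- SAP 4.3 sets the size of the trial: "Approximately 160 subjects will be randomized to the four treatment groups".
- SAP 4.2 limits one region: "Enrollment in Japan will be capped at 10% of subjects (4 subjects per group"). There is no minimum.
- Protocol 5.2.1 sets the age range: "Adult male or female, ≥ 18 and ≤ 75 years old at Screening". The top age class therefore spans only 65 to 75.

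Protocol 8.1.5.2 plans the same six factors for EASI 75 and IGA 0/1 without any size condition. SAP 12.1 does not list the size rule among the changes from the protocol.

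**The concern.** A minimum class size is sensible, because an estimate from three or four people is of no use. Here, though, the rule acts on the factor and not on the class. If three subjects have a BMI of 40 or over, the results for the other three BMI classes also disappear, however well filled those are. Neither document provides for merging the sparse class or leaving it out alone.

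At stake is whether the trial shows, as SAP 10.7 intends, how the effect varies with BMI, age and race. If a factor is lost, the sponsor must either report nothing for it or choose new groupings once the distribution is known. A merging rule is better fixed in the SAP, which Protocol 8.1 requires to be final before database lock and blind break.

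**Working it through.** **Inputs.** Total about 160 and 40 per group (SAP 4.3); threshold of fewer than 5 (SAP 10.7); classes from SAP Table 14; Japan cap of 10% (SAP 4.2). The documents do not give the expected share of subjects with BMI 40 or over, aged 65 or over, or of race Other. I therefore take the share p as an assumption and vary it.

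**The plan's own figures.** The plan states no figure for the subgroup rule. Its pairwise power statement confirms the sample size. With assumed means of "35, 45, 60, and 70 in the placebo, 7.5 mg, 15 mg, and 30 mg arms" and SD 40, the standard error of a difference is 40 × √(2/40) = 8.94. Then:

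- 30 mg versus placebo: Φ(35/8.94 − 1.96) = 97.5%, or 97.2% by noncentral t; the plan says 97%.
- 15 mg versus placebo: Φ(25/8.94 − 1.96) = 79.8%, or 78.8% by noncentral t; the plan says 78%.

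Both agree to within 2 points.

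**How the 5 is counted.** SAP 10.7 defines the subgroups by each demographic factor, and Table 14 has no treatment-arm dimension. The natural count is therefore over all arms, although the SAP does not say so.

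**Chance that a class triggers the rule.** With X the number of subjects in the class, X ~ Binomial(160, p) and

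P(X ≤ 4) = Σ (k = 0 to 4) C(160, k) p^k (1 − p)^(160 − k).

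For p = 0.03 the five terms are 0.008 + 0.038 + 0.093 + 0.152 + 0.184, which sum to 0.474 before rounding of the terms. Over the range:

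| Assumed share | Expected count (160 × p) | P(fewer than 5) |
|---|---|---|
| 1% | 1.6 | 97.7% |
| 2% | 3.2 | 78.2% |
| 3% | 4.8 | 47.4% |
| 4% | 6.4 | 22.9% |
| 5% | 8.0 | 9.4% |
| 6% | 9.6 | 3.4% |
| 10% | 16.0 | 0.02% |

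The chance is 50% at a share of about 2.9%. It falls below 10% at about 5%.

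**Region.** At the cap Japan has 0.10 × 160 = 16 subjects. Since 16 ≥ 5, the rule is not triggered. Because the cap has no floor, region would be lost only if Japan enrolled 4 or fewer in total.

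**What is lost when the rule fires.** The sparse class holds at most 4 subjects, 4/160 = 2.5% of the trial. The rule also removes that factor's results for the remaining 160 − 4 = 156.

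**The case against.** The strongest reply is that the problem may never arise. Nothing in the documents shows that any Table 14 class is rare, and from a share of 6% upward the chance is 3% or less. For age in particular, eligibility runs to 75 and nothing suggests a share below 5%. This stands, and it is why age is only a possible case.

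Other safeguards exist. SAP 10.7 allows further subgroup analyses on baseline characteristics, which could include coarser classes. SAP 10.5 separately summarises EASI, IGA and pruritus NRS for Japan. The median split of weight is effectively immune to the rule and gives related information if BMI is lost. These soften the loss, but the extra analyses are optional and not pre-specified, and the Japan summary says nothing about the other two regions. It can also be said that presentation is conditional from the outset, because the size rule stands in the same section as the plan. That is fair for the primary endpoint. The protocol's commitment for EASI 75 and IGA 0/1 has no such condition.

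A reader might infer something stronger: that region, the Period 1 stratification factor, is lost by design because Japan is limited to 4 per group. That needs the 5 to be counted within each arm, where 4 × 5 = 20 Japanese subjects would be required against a cap of about 16. On that count a class with a 10% share would also fall below 5 in at least one of four arms with probability 1 − (1 − 0.629)^4 = 98%. The documents do not support this reading, since the subgroups are defined without reference to arm. Nor would the 98% describe Japan: it treats arm counts as independent binomial draws, whereas randomization is stratified by region.

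**Conclusion.** The point holds as a minor one. The rule removes a whole factor because of one sparse class, and no other text in the protocol or SAP limits it to that class. Counted over all arms, the chance for a given class is 78%, 47%, 23%, 9% or 3% at assumed shares of 2%, 3%, 4%, 5% or 6%. Which of these applies is unknown, because the documents give no expected shares. BMI (40 or over) and race (Other) are exposed, and age (65 or over) possibly so. Region is at risk only if Japan enrols 4 or fewer in total.

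The conclusion rests on two assumptions: about 160 subjects are randomized, and the 5 is counted over all arms. These are supportive Phase 2b subgroup analyses without multiplicity adjustment (SAP 10.6), and the primary MCP-Mod result is unaffected.

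**What to change.** Replace the size rule in SAP 10.7 with:

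> The count is taken over all treatment groups. If a category has fewer than 5 subjects, only that category is affected: for ordered factors it is merged with the adjacent category (BMI 40 or over into 30 or over; age 65 or over into 40 or over), and for race and region it is omitted from the comparison and the remaining categories are presented. The factor is dropped only if fewer than two categories remain.

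List the rule in SAP 12.1, since Protocol 8.1.5.2 has no size condition.

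The trigger should stay on the total count. A trigger of fewer than 5 in any one arm would, by the 98% above, almost always collapse a 10% class that the present rule would show.

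The cost is a few sentences of text and coarser classes where merging occurs. For race and region, up to 4 subjects would not appear under their own category. The change does not cure thin data: a class of exactly 5 averages 5/4 = 1.25 subjects per arm and would still be shown, so counts by arm should accompany each result.

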**Table 14. Subgroup Analysis**

Subgroup Factor	Categories
Age	< 40 years old ≥ 40 – < 65 years ≥ 65 years old
Sex	Male Female
BMI	< 25 ≥ 25 – < 30 ≥ 30 – < 40 ≥ 40
Race	White Asian Other
Weight	< median ≥ median
Geographic region	US/PR/Canada EU/AUS Japan

## **11.0 Safety Analysis**

### **11.1 General Considerations**

Safety analyses will include adverse events, laboratory, and vital sign measurements. Safety summaries will be provided using the safety population in each period. Comparison between each upadacitinib group and placebo group will be performed for change from baseline laboratory and vital sign parameters in the Safety\_1 Population, using one-way ANOVA.

Missing safety data will not be imputed.

### **11.2 Analysis of Adverse Events**

Treatment-emergent adverse events (TEAEs) will be summarized in each period.

Pre-treatment adverse event and protocol-defined non SAE will be presented in a data listing. TEAEs will also be summarized separately for the time period when subjects receive upadacitinib monotherapy of each dose level across Period 1 and Period 2, the time period when subjects receive concomitant mometasone furoate, and the time period when subjects receive concomitant triamcinolone acetonide.

